6.2.2 Handling of other treatment

Not applicable.

6.2.3 Instruction for prescribing and taking study treatment

There should be a period of at least 1 hour after the infusion whereby the participant requires close observation. Patient care should be managed as per local medical practice.

6.3 Measures to minimize bias: randomization and blinding

6.3.1 Treatment assignment, randomization

At randomization visit (Day 1), all eligible participants will be randomized via IRT to one of the treatment arms. The investigator or his/her delegate will contact the IRT after confirming that the participant fulfills all the inclusion/exclusion criteria. The IRT will assign a randomization number to the participant, which will be used to link the participant to a treatment arm and will specify unique medication numbers of study treatment TIN816 to be administered to the participant or placebo treatment administered as 0.9% saline solution, sourced locally.

The randomization numbers will be generated using the following procedure to ensure that treatment assignment is unbiased and concealed from participants and investigator staff. A participant randomization list will be produced by the IRT provider using a validated system that automates the random assignment of participant numbers to randomization numbers. These randomization numbers are linked to the different treatment arms, which in turn are linked to medication numbers. A separate medication list will be produced by or under the responsibility of Novartis Global clinical supply (GCS) using a validated system that automates the random assignment of medication numbers to packs containing the study treatment.

The randomization scheme for participants will be reviewed and approved by a member of the Randomization Office.

6.3.2 Treatment blinding

Participants, investigator staff, and persons performing the assessments will remain blind to the identity of the treatment from the time of randomization until database lock. All unblinded personnel will keep randomization lists and data or information that could unblind other study team members confidential and secure except as described below.

Novartis Clinical Trial Team (CTT), including sample analyst(s) (PK, PD [REDACTED]) will be unblinded to the identity of treatment and will have full access to trial data.

Site staff

With the exception of any unblinded site staff identified below, all site staff (including study investigator and study nurse) will be blinded to study treatment throughout the study.

Unblinding a single participant at site for safety reasons (necessary for participant management) will occur via an emergency system in place at the site.

Sponsor staff

In addition to Novartis CTT, the following unblinded sponsor roles are required for this study.

- Unblinded field monitor(s)
- Unblinded clinical staff managing drug re-supply to site

The unblinded field monitors are required to review drug accountability and allocation at site. The unblinded monitors are not provided with a randomization list directly but will be unblinded through review of source documentation compiled by the unblinded pharmacist, which details treatment allocation to individual participants. The unblinded monitors will also be able to review the treatment allocation provided by IRT to the unblinded pharmacist.

If sponsor clinical staff are required to assist in the management and re-supply of investigational drug product, these individuals are not provided with randomization lists directly, but may be unblinded through communication of drug re-supply needs via the unblinded site pharmacists.

The sample analysts will receive a copy of the randomization schedule (via request to the Randomization Office), to facilitate analysis of the samples. The sample analysts will provide the sample data to the study team.

The study statistician will be able to access the full randomization list from the start of the study and is allowed to share unblinded information with the rest of the clinical trial team as appropriate for internal decision purposes. For example, unblinded summaries and unblinded individual data can be shared with the team whenever necessary.

Study programmers and other personnel involved in study data analysis [REDACTED] are allowed to access treatment assignment information from the start of the study for the purpose of data analysis.

The clinical trial team is allowed to share unblinded results with other sponsor staff (e.g. decision boards) and to an external Steering Committee, as required for internal decision making on the study or the project at the time of interim analyses while the study is ongoing.

Following final database lock all roles may be considered unblinded.

Table 6-2 Blinding and unblinding plan

Role	Time or Event		
	Randomization list generated	Treatment allocation & dosing	Safety event (single subject unblinded)
Participants	B	B	B
Site Staff	B	B	UI
Unblinded site staff, e.g. pharmacy staff	B	UI	B
Sponsor CTT	B	UI	UI
All other Sponsor staff not identified above (i.e. project team, management & decision boards, support functions)	B	UI	UI
Independent committees used for assessing interim results, if required (e.g. DMC)	B	UI	UI

B Complete blinded

UI Unblinded to individual participant treatment codes

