6.8 Concomitant and other therapy

6.8.1 Concomitant therapy

All medications, procedures, and significant non-drug therapies (including physical therapy and blood transfusions) administered after the participant was enrolled into the study must be recorded on the appropriate eCRFs.

Each concomitant drug must be individually assessed against all exclusion criteria/prohibited medication. If in doubt, the investigator should contact the Novartis medical monitor before randomizing a participant or allowing a new medication to be started. If the participant is already enrolled, contact Novartis to determine if the participant should continue participation in the study.

Prior medications related to the treatment of sepsis and AKI taken within 2 weeks prior to screening will be recorded on the eCRF.

Administered resuscitation fluids should only be recorded as total daily volume in the concomitant eCRFs. Blood products should be recorded separately.

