10.2.2 Definitions

Additional treatment	Medicinal products that may be used during the clinical trial as described in the protocol, but not as an investigational medicinal product (e.g. any background therapy)
Assessment	A procedure used to generate data required by the study
AUC _{inf}	The AUC from time zero to infinity (mass \times time \times volume $^{-1}$)
AUC _{last}	The AUC from time zero to the last measurable concentration sampling time (t _{last}) (mass \times time \times volume $^{-1}$)
Biologic Samples	A biological specimen including, for example, blood (plasma, serum), saliva, tissue, urine, stool, etc. taken from a study participant
Cl	The total body clearance of drug from the serum following intravenous administration (volume \times time $^{-1}$)
Clinical Outcome Assessment (COA)	A measure that describes or reflects how a participant feels, functions, or survives
Clinical Trial Team	A group of people responsible for the planning, execution and reporting of all clinical trial activities. Examples of team members include the Study Lead, Medical Monitor, Trial Statistician etc.
C _{max}	The maximum (peak) observed serum drug concentration after single dose administration (mass \times volume $^{-1}$)
Coded Data	Personal Data which has been de-identified by the investigative center team by replacing personal identifiers with a code.
Cohort	A group of individuals who share a common exposure, experience or characteristic, or a group of individuals followed-up or traced over time

Control drug	A study intervention (active or placebo) used as a comparator to reduce assessment bias, preserve blinding of investigational drug, assess internal study validity, and/or evaluate comparative effects of the investigational drug
Discontinuation from study	Point/time when the participant permanently stops receiving the study treatment and further protocol required assessments or follow-up, for any reason. No specific request is made to stop the use of their samples or data.
Discontinuation from study treatment	Point/time when the participant permanently stops receiving the study treatment for any reason (prior to the planned completion of study intervention administration, if any). Participant agrees to the other protocol required assessments including follow-up. No specific request is made to stop the use of their samples or data.
Dosage	Dose of the study treatment given to the participant in a time unit (e.g. 100 mg once a day, 75 mg twice a day)

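### Section 6.3.2 does not ensure that upcoming assignments are concealed from the medical monitor, whom sites may consult before randomizing

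*Protocol*

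**What the plan says.** Protocol section 6.3.1 describes assignment through the IRT and gives the aim of the procedure as "to ensure that treatment assignment is unbiased and concealed from participants and investigator staff". Sponsor staff are outside that aim.

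Section 6.3.2 opens with a general rule: "All unblinded personnel will keep randomization lists and data or information that could unblind other study team members confidential and secure except as described below". What follows includes these provisions:

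- The clinical trial team (CTT), with the sample analysts counted in it, "will be unblinded to the identity of treatment and will have full access to trial data".
- On the statistician: "The study statistician will be able to access the full randomization list from the start of the study and is allowed to share unblinded information". The sharing is "with the rest of the clinical trial team as appropriate for internal decision purposes", and the example given is that "unblinded summaries and unblinded individual data can be shared with the team whenever necessary".
- Sample analysts receive a copy of the randomization schedule. Programmers and other analysis staff may see treatment assignment information from the start.
- Field monitors and drug re-supply staff, although they may become unblinded, are expressly not handed a randomization list.

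Section 10.2.2 defines the CTT: "Examples of team members include the Study Lead, Medical Monitor, Trial Statistician etc". Section 6.8.1 says that, if a concomitant drug is in doubt against the exclusion criteria or prohibited medication, "the investigator should contact the Novartis medical monitor before randomizing a participant". Table 6-2 shows the Sponsor CTT as blinded when the list is generated and as unblinded to individual codes at treatment allocation and dosing.

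**The concern.** A full list held from the start contains assignments that have not yet been used. Concealment requires that nobody who can affect whether a given patient enters knows, or can work out, the next assignment. IRT allocation protects against this only while the list stays out of reach of such people.

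Here the list holder, the schedule holders and the medical monitor belong to one unblinded team, and the monitor may be asked about a patient before that patient is randomized. The subject of that consultation is also relevant. Concomitant drugs include antiplatelet and anticoagulant agents, and bleeding is an adverse event of special interest (section 8.6.6). At stake is the comparability of the two arms in the secondary objective, safety and tolerability versus placebo.

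**Working it through.** **Step 1: who can hold what, and who advises on entry.**

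| Role | Access under 6.3.2 | Contact with entry decisions |
|---|---|---|
| Study statistician | Full list from the start | None stated |
| Sample analysts | Copy of the randomization schedule | None stated |
| Programmers, analysis staff | Assignment information from the start | None stated |
| Medical monitor (CTT member, 10.2.2) | Unblinded as part of the CTT; may receive individual data | Consulted before randomization on concomitant drugs (6.8.1) |
| Field monitors, re-supply staff | Expressly not given the list directly | None stated |

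The restriction in the last row is not repeated for the CTT. No section separates unused assignments from the medical monitor.

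**Step 2: text against Table 6-2.** The statistician is a CTT member. The text gives the statistician the list from study start, while the table shows the CTT unblinded only at allocation and dosing. The two can be read together if the list is generated before the study starts, since section 10.2.2 defines the start as the first signed consent. Even so, the table has no entry for access between study start and each participant's allocation, which is the interval that matters for concealment.

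**Step 3: arm sizes.** About 20 participants at 3:1 (section 4.1) gives 20 × 3/4 = 15 on TIN816, matching section 9.9.1, and 20 − 15 = 5 on placebo. One participant is 1/5 = 20% of the placebo arm and 1/15 = 6.7% of the TIN816 arm. These are arm fractions. They are not estimates of bias.

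**Step 4: does withholding the list suffice?** Section 6.3.2 permits sharing individual data, so suppose that the monitor knows only the past codes. The documents give no block size, so it is assumed here, with one unstratified list. In a permuted block with *a* TIN816 and *p* placebo slots, the next assignment is certain once all remaining slots belong to one arm. The expected number of such slots per block is the expected length of the final run: a/(p+1) + p/(a+1).

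| Assumed scheme | Certain slots per block | Share | Of 20 slots |
|---|---|---|---|
| Blocks of 4 (3:1) | 3/2 + 1/4 = 1.75 | 1.75/4 = 44% | 8.75 |
| Blocks of 8 (6:2) | 6/3 + 2/7 = 2.29 | 2.29/8 = 29% | 5.7 |
| One block of 20 (15:5) | 15/6 + 5/16 = 2.81 | 2.81/20 = 14% | 2.8 |
| Simple randomization | 0 | 0% | 0 |

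Exact enumeration of the blocked sequences gives the same shares. A holder of the full list knows all 20. Withholding the list therefore helps but, under blocking, does not by itself restore concealment.

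**The case against.** A reader might infer that the list may be passed to the medical monitor, or that allocation is in fact not concealed from the monitor. The documents do not support either reading. Section 6.3.2 permits sharing of unblinded information for internal decisions, illustrated by summaries and individual data. It does not name the list as shareable, and its general rule is that lists stay confidential. No section gives the monitor unused assignments.

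A reader might also infer that the monitor rules on eligibility in general. Section 6.8.1 covers only doubts about concomitant drugs. The investigator confirms all criteria before contacting the IRT (6.3.1), may apply no additional criteria and may not depart from any (section 5), and waivers are excluded (section 8). Section 8.4.4 adds consultation with the sponsor on out-of-range laboratory values, but the decision remains the investigator's. The room to steer entry is narrow.

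Sponsor unblinding is also deliberate. The study is blinded to participants and investigators only, and the PK and interim work needs treatment codes.

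All of this stands, and it limits the point. It does not answer it: the work on treated participants does not need assignments not yet used, and the protocol states a list restriction for two other sponsor roles but not for the team that includes the monitor.

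**Conclusion.** The point holds as a gap in assurance. The protocol does not ensure that upcoming assignments are concealed from a person who can influence entry, and the statistician's access from the start does not sit clearly with Table 6-2. It does not show that concealment is broken.

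The consequence is limited. Sections 9.2.1 and 9.3 plan descriptive analyses only. The primary endpoint is PK in TIN816 recipients, so it could be affected only through which patients enter that arm. The main exposure is the safety description of about 15 versus 5. No probability, direction or size of bias can be derived from the documents. The predictability figures rest on assumed block sizes and on past codes being known as enrolment proceeds. This is an inexpensive improvement and does not threaten the primary objective or change the sample size.

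**What to change.** In section 6.3.2:

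1. Keep unused assignments with the IRT provider and the Randomization Office.
2. Limit the statistician, programmers, sample analysts and the rest of the CTT to codes of participants already randomized and dosed.
3. State that anyone giving pre-randomization advice has no access to unused assignments and, because past codes can reveal the next one under blocking, no individual-level codes while enrolment is open.
4. Align Table 6-2 with the text. The table marks all other sponsor staff as unblinded at allocation and dosing too, so the adviser in item 3 needs a separate row.

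Section 6.8.1 should then direct pre-randomization queries to that adviser. The medical monitor can keep code access for other work.

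The cost is protocol wording, an IRT access setting and the assignment of these queries to an existing sponsor physician without code access. PK assay work and the interim analysis after Day 14 use only dosed participants, so neither is affected.

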6.3.3 Emergency breaking of assigned treatment code

Emergency code breaks must only be undertaken when it is required to in order to treat the participant safely.

Most often, knowledge of the possible treatment assignments are sufficient to treat a study participant who presents with an emergency condition. Emergency treatment code breaks are performed using the IRT. When the investigator contacts the system to break a treatment code for a participant, he/she must provide the requested participant identifying information and confirm the necessity to break the treatment code for the participant. The investigator will then receive details of the investigational drug treatment for the specified participant and a fax or email confirming this information. The system will automatically inform the Novartis monitor for the site and the study team that the code has been broken.

It is the investigator's responsibility to ensure that there is a dependable procedure in place to allow access to the IRT system at any time in case of emergency. The investigator will provide:

- protocol number
- participant number

In addition, oral and written information to the participant must be provided on how to contact his/her backup in cases of emergency, or when he/she is unavailable, to ensure that un-blinding can be performed at any time.

A participant can continue participation in the study in the event of an unblinding incident.

6.4 Study treatment compliance

An one time intravenous infusion will be administered in the ICU/HDU. This information must be captured in the source document, the appropriate eCRF and in the Drug Accountability Log. The site personnel should reflect total volume administered as well as the date and time of administration in the eCRF page. Any reason for dose interruption of the IV infusion will also be captured in the source document and the eCRF.

PK parameters (measures of treatment exposure) will be determined in all participants treated with TIN816, as detailed in PK section ([Section 8.7](#)).

6.4.1 Recommended treatment of adverse events

At present there is insufficient information to provide specific recommendations regarding treatment of AEs. There is also no specific antidote to the study drug. Investigators should use their best clinical judgement and follow local treatment guidelines in treating adverse events.

Medication used to treat AEs must be recorded on the appropriate eCRF.

6.5 Dose modification

Investigational or other study treatment dose adjustments are not permitted as this is an one-time IV dose administration.

6.6 Continued access to study treatment after the end of the study

Not applicable for this PK study of a single dose IV infusion investigational drug.

6.6.1 Post trial access

Not applicable for this PK study of a single dose IV infusion investigational drug.

6.7 Treatment of overdose

Study treatment overdose is the administration of a quantity of the investigational medicinal product which is above the maximum recommended dose according to study protocol.

In the event of an overdose, the treating physician, in collaboration with the investigator should:

- Contact the medical monitor immediately.
- Closely monitor the participant for any AE/SAE and laboratory abnormalities until study drug can no longer be detected systemically (at least 38 days).
- Obtain a plasma sample for PK analysis (within 15 minutes after infusion interruption or infusion end, the latter marking the first PK time point post-dose).
- Document the quantity of the excess dose.

6.7.1 Reporting of study treatment errors including misuse/abuse

Medication errors are unintentional errors in the prescribing, dispensing, administration or monitoring of a medicine while under the control of a healthcare professional, participant or consumer (EMA definition).

Misuse refers to situations where the medicinal product is intentionally and inappropriately used not in accordance with the protocol.

Abuse corresponds to the persistent or sporadic, intentional excessive use of a medicinal product, which is accompanied by harmful physical or psychological effects.

Study treatment administration errors and uses outside of what is foreseen in the protocol will be recorded on the appropriate eCRF irrespective of whether or not associated with an AE/SAE. Study treatment errors will be collected and reported in the safety database irrespective of it being associated with an AE/SAE within 24 hours of investigator's awareness. For more information on AE and SAE definition and reporting requirements, please see the respective sections.

6.8 Concomitant and other therapy

6.8.1 Concomitant therapy

All medications, procedures, and significant non-drug therapies (including physical therapy and blood transfusions) administered after the participant was enrolled into the study must be recorded on the appropriate eCRFs.

Each concomitant drug must be individually assessed against all exclusion criteria/prohibited medication. If in doubt, the investigator should contact the Novartis medical monitor before randomizing a participant or allowing a new medication to be started. If the participant is already enrolled, contact Novartis to determine if the participant should continue participation in the study.

Prior medications related to the treatment of sepsis and AKI taken within 2 weeks prior to screening will be recorded on the eCRF.

Administered resuscitation fluids should only be recorded as total daily volume in the concomitant eCRFs. Blood products should be recorded separately.

6.8.1.1 Permitted concomitant therapy requiring caution and/or action

Administration of nephrotoxic drugs such as contrast agents, NSAIDs, angiotensin-converting enzyme (ACE) inhibitors, amphotericin B, high doses of loop diuretics, anti-microbial drugs like acyclovir and aminoglycoside drugs should be avoided or used with caution, as recommended in the KDIGO Clinical Practice Guideline for AKI ([KDIGO \(2012\)](#)).

In addition, based on the mechanism of action of TIN816 (removal of ADP and inhibition of P2Y12 activation), there is a theoretical bleeding risk. Although no relevant bleeding complications were observed in the preclinical toxicology and FIH study at exposure resulting in a full inhibition of ADP/thrombin-induced platelet aggregation, an additive inhibitory effects of platelet aggregation caused by TIN816 was found in the presence of antiplatelet drugs (ticagrelor or acetylsalicylic acid) at a clinical therapeutic dose. Thus, careful monitoring of coagulation/clinical signs of bleeding should occur if antiplatelet agents or other anticoagulant drugs are used concomitantly during the study. Management of bleeding in patients treated with TIN816 may include temporary discontinuation of antiplatelet or anticoagulant drugs, resuscitation with intravenous fluid, packed red cell transfusion and platelet transfusions, as per local practice.

